7.3.4.1 Adverse Events

All AEs and SAEs will be collected at the time points specified in Table 4 from the time of informed consent completion until study participation is complete. Any preexisting medical conditions or signs/symptoms present in a subject prior to obtaining the informed consent are not considered AEs in the study and should be recorded in the Medical History section of the eCRF. See Section 9.2 and 9.3 for further details.

7.3.4.2 Slit Lamp Biomicroscopy

Slit lamp biomicroscopy assessments will be performed using the ISO11980 grading at the Screening/Baseline visit (D1) and at Visit 3 (and at unscheduled and early exit visits, as necessary).

A biomicroscopy examination of the cornea, adnexa and anterior segment of the eye will be performed, OD and OS, at the Screening/Baseline visit (D1) and at Visit 3 (and at unscheduled and early exit visits, as necessary), and recorded on eCRFs. Record both eyes for the same subject if both are noted to have such a finding.

If warranted, a short slit lamp video or slit lamp photograph should be recorded to demonstrate any abnormal findings or findings of interest during biomicroscopy (for example inferior arcuate staining). Record both eyes for the same subject if both are noted to have such a finding.

- Limbal hyperemia (All Subjects)

Limbal hyperemia (redness) will be recorded on a 5-point scale as follows:

0 = None	No hyperemia
1 = Trace	Slight limbal hyperemia (mild segmented)
2 = Mild	Mild limbal hyperemia (mild circumcorneal)
3 = Moderate	Significant limbal hyperemia (marked segmented)
4 = Severe	Severe limbal hyperemia (marked circumcorneal)

- Bulbar Hyperemia (All Subjects)

Bulbar conjunctival hyperemia (redness) will be recorded on a 5-point scale as follows:

0 = None	No hyperemia
1 = Trace	Slight regional hyperemia
2 = Mild	Diffuse hyperemia
3 = Moderate	Marked regional or diffuse hyperemia
4 = Severe	Diffuse episcleral or scleral hyperemia

- Corneal Epithelial Edema (All Subjects)

Corneal epithelial edema should be classified according to the number of microcysts observed. The presence/absence of fluid-filled or debris-filled cysts should be documented.

0 = None	No microcysts; normal transparency
1 = Trace	1 to 20 microcysts; barely discernable local epithelial haziness
2 = Mild	21 to 50 microcysts; faint but definite localized or generalized haziness
3 = Moderate	51 to 100 microcysts; significant localized or generalized haziness
4 = Severe	> 100 microcysts; definite widespread epithelial cloudiness giving a dull glass appearance to the cornea or numerous coalescing bullae

- Corneal Stromal Edema (Group 2)

Corneal stromal edema will be recorded on a 5-point scale as follows:

0 = None	No edema
1 = Trace	Just detectable clouding
2 = Mild	Faint corneal striae (2 or fewer)

3 = Moderate	Pronounced corneal striae (3)
4 = Severe	Folds in descemet's membrane and ≥ 4 pronounced striae

- Corneal Vascularization (All Subjects)

Corneal vascularization will be recorded on a 5-point scale as follows:

0 = None	No vessel penetration
1 = Trace	< 1.00 mm vessel penetration
2 = Mild	≥ 1.00 mm to ≤ 1.5 mm vessel penetration
3 = Moderate	> 1.5 mm to ≤ 2.0 mm vessel penetration
4 = Severe	Vessel penetration > 2.0 mm

- Conjunctival Compression/Indentation (Group 2)

Bulbar conjunctival compression/indentation will be recorded on a 2-point scale as follows:

0 = Absent

1 = Present

- Chemosis (All Subjects)

Chemosis will be recorded on a 2-point scale as follows:

0 = Absent

1 = Present

- Corneal Infiltrates (Group 2)

The severity of corneal infiltrates will be recorded on a 5-point scale as follows:

0 = None	No infiltrates
1 = Trace	Single or multiple epithelial infiltrates < 1 mm in diameter
2 = Mild	Single or multiple epithelial infiltrates ≥ 1 mm and < 2 mm in diameter
3 = Moderate	Multiple infiltrates ≥ 2 mm and < 3 mm in diameter
4 = Severe	Multiple dense infiltrates ≥ 3 mm in diameter

The location of infiltrates observed should be recorded in the source document, as indicated in Figure 2. In addition, the “Infiltrates” form should be completed including:

- Eye (OD, OS)
- Location (Central, Peripheral Superior, Peripheral Inferior, Peripheral Nasal, Peripheral Temporal)
- Type (Focal, Diffuse)
- Depth of Largest Infiltrate (Epithelial, Anterior Stromal, Mid/Posterior Stromal)
- Number of Infiltrates (1, 2, 3, 4, 5, 6, 7, >7)
- Size of the largest infiltrate (in mm)

Additional findings (e.g., ‘Presence and type of discharge’ or ‘Degree of overlying epithelial defect’) should be captured in the corresponding Biomicroscopy panel, or AE Form (if applicable).

- Corneal Staining (All Subjects)
 - Corneal Staining Set Up

All corneal staining observations should be carried out using a blue excitation light to full intensity and magnification at 16x in conjunction with a yellow barrier filter in the observation system (approximate beam width 10 mm and height 8 mm).

Apply one drop of fresh, non-preserved, sterile saline to the tip of a Sodium Fluorescein (NaFl) impregnated strip. Allow saline to drip off the strip (i.e., without a shaking motion).

Ask the subject to look up and nasally. Gently retract the lower lid and touch the strip to the inferior temporal bulbar conjunctiva, approximately 5 mm or more from the limbus, for 1 to 2 seconds, so that 1 to 2 mm of the flat side of the strip makes contact with the ocular surface. Withdraw the strip and release the lower lid.

[figure not shown]
- Corneal Staining - Standard Assessment

Record grade according to the following scale:

0 = None	No staining
1 = Trace	Minimal superficial staining or punctate staining a) Dimpling, discrete dot staining, or b) Trace superficial lens insertion marks or foreign body tracks
2 = Mild	Regional or diffuse punctate staining a) Central or generalized, or b) Peripheral including 3 to 9 o'clock staining, or c) Foreign body tracks
3 = Moderate	Dense coalescent staining up to 2 mm in diameter a) Corneal abrasion b) Foreign body track
4 = Severe	Dense coalescent staining greater than 2 mm in diameter

The location of staining observed should be recorded in source documentation only, as indicated in Figure 2:

Figure 2. Corneal Regions for Recording Location

Recurrent erosion and corneal ulceration should be recorded under “Other findings.”

Inferior arcuate staining should be recorded under “Other findings.”

- **Conjunctival Staining (All Subjects)**

Conjunctival staining should be assessed immediately after corneal staining. Therefore, an additional application of NaFl is not required. However, if needed in order to make a sound judgment, one more application can be made following the instructions given in the section above and using a new NaFl strip. All conjunctival staining observations should be carried out using a blue excitation light in conjunction with a yellow barrier filter in the observation system after NaFl instillation.

Conjunctival staining will be assessed on a 5-point scale:

0 = None	No staining
1 = Trace	Minimal regional staining
2 = Mild	Regional or diffuse punctate staining
3 = Moderate	Significant dense coalescent staining
4 = Severe	Severe dense geographical staining

- **Palpebral conjunctival observations (All Subjects)**

The severity of the maximal palpebral conjunctival response will be recorded on a 5-point scale as follows:

0 = None	Uniform satin appearance of the conjunctiva
1 = Trace	Slight conjunctival injection without texture
2 = Mild	Mild or scattered papillae/follicles less than 1 mm in diameter
3 = Moderate	Significant papillae/follicles less than 1 mm in diameter, and/or marked conjunctival injection Staining of the top of one papilla
4 = Severe	Localized or generalized papillae/follicles 1 mm or more in diameter Staining of the top of more than one papilla

- Other Findings (All Subjects)

Record any other finding(s) and use the following scale to grade severity:

0 = None	No other significant biomicroscopic findings
1 = Trace	Minimal findings
2 = Mild	Mild findings
3 = Moderate	Significant findings
4 = Severe	Severe findings

Note: If there are multiple other findings, on the eCRF for “Other” record the grade of the most severe in the “Result” field and record all findings (along with their individual grades) in the “If Other, Specify” field.

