6.3.3. Biomicroscopy Findings

Slit lamp biomicroscopy assessments will be performed using the ISO11980 grading at the Screening/Baseline visit (Day 1) and at Visit 3 (and at unscheduled and early exit visits, as necessary).

Biomicroscopy parameters will be summarized [eye-level summary] using descriptive statistics by analysis visit:

- Limbal Hyperemia: None, Trace, Mild, Moderate and Severe.
- Bulbar Hyperemia: None, Trace, Mild, Moderate and Severe.
- Corneal Epithelial Edema: None, Trace, Mild, Moderate and Severe.
- Corneal Stromal Edema (only Group 2): None, Trace, Mild, Moderate and Severe.
- Corneal Vascularization: None, Trace, Mild, Moderate and Severe.
- Conjunctival Compression/Indentation (only Group 2): Absent, Present.
- Chemosis: Absent, Present.
- Corneal Infiltrates (only Group 2): None, Trace, Mild, Moderate and Severe.
 - Central: Yes, No.
 - Peripheral Superior: Yes, No.
 - Peripheral Inferior: Yes, No.
 - Peripheral Nasal: Yes, No.
 - Peripheral Temporal: Yes, No.
 - Type: Focal, Diffuse.
 - Depth of Largest Infiltrate: Epithelial, Anterior stromal, Mid/posterior stromal.
 - Number of Infiltrates: 1, 2, 3, 4, 5, 6, 7, ≥ 8 .
 - Size of the Largest Infiltrate (mm).
- Corneal Staining: Absent, Present.
 - Central: None, Trace, Mild, Moderate and Severe.

- Superior: None, Trace, Mild, Moderate and Severe.
- Nasal: None, Trace, Mild, Moderate and Severe.
- Inferior: None, Trace, Mild, Moderate and Severe.
- Temporal: None, Trace, Mild, Moderate and Severe.
- Conjunctival Staining: None, Trace, Mild, Moderate and Severe.
- Palpebral Conjunctival Observations: None, Trace, Mild, Moderate and Severe.
- Other Findings: None, Trace, Mild, Moderate and Severe.

Shift tables will be generated using the ISO11980 grading categories. The number and percentage of eyes shifting from categories between Baseline and Visit 3 will be summarized.

A supportive listing for biomicroscopy assessments will be provided.

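### The pooled shift of Other findings can show a new, different sign, corneal ulceration included, as no change from Baseline

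*Protocol*

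**What the plan says.** Protocol 7.3.4.2 grades most slit-lamp signs on scales of their own. Some corneal signs have no item and are sent to Other findings: "Recurrent erosion and corneal ulceration should be recorded under" that heading, and likewise "Inferior arcuate staining should be recorded under" it.

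Other findings uses a generic severity scale from 0 to 4 that is not tied to any condition: "Record any other finding(s) and use the following scale to grade severity". Where there are several, the site must "record the grade of the most severe in the" *Result* field. The separate terms, each with its own grade, are kept only as free text under *If Other, Specify*.

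SAP 6.3.3 summarizes this item at eye level as one variable, "Other Findings: None, Trace, Mild, Moderate and Severe". On shifts it says: "The number and percentage of eyes shifting from categories between Baseline and Visit 3 will be summarized". The table list in SAP Section 13 has one general biomicroscopy summary (14.3.3.1) and one general shift table (14.3.3.2). Corneal staining has its own summary and shift (14.3.3.3 and 14.3.3.4), and infiltrates have their own summary (14.3.3.5). No table reports Other findings by term.

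**The concern.** A shift table is meaningful when both grades describe the same sign. For limbal hyperemia or corneal vascularization they do. For Other findings, the Baseline grade may belong to one condition and the Visit 3 grade to another, and nothing in the tabulated value tells the reader which.

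A Baseline Other finding is plausible. The protocol states: "A biomicroscopy examination of the cornea, adnexa and anterior segment of the eye will be performed, OD and OS". Yet it gives no graded lid item, so a lid finding would presumably be entered under Other. Such a finding occupies the Baseline cell and sets the grade that any new sign must exceed before the table shows worsening.

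Biomicroscopy is a named safety endpoint in its own right (protocol 6.3.3, SAP 6.1). The row in question is the one that holds corneal ulceration and recurrent erosion. If it cannot show a new finding reliably, the summary of that endpoint is weakest for the signs it has no other row for.

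**Working it through.** The plan gives no figure for this point, so there is none to reproduce. The check follows the recording rule through to the shift cell.

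**Inputs**
- Grade of the Baseline Other finding, b = 1 to 4 (generic scale, protocol 7.3.4.2).
- Grade of a new, different Other finding at Visit 3, u = 1 to 4 (same scale).
- Tabulated grade at a visit = highest grade present in the eye at that visit (rule for *Result*, protocol 7.3.4.2).
- Shift = tabulated grade at Visit 3 compared with b (SAP 6.3.3, Table 14.3.3.2).

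**Tabulated grade at Visit 3**
- Baseline finding persists at grade b: max(b, u).
- Baseline finding has resolved: u.

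**All 4 × 4 = 16 pairings**

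| | u > b | u = b | u < b |
|---|---|---|---|
| Number of pairings | 6 | 4 | 6 |
| Baseline finding persists | worsening | no change | no change |
| Baseline finding resolved | worsening | no change | improvement |
| Shift by term (new sign goes from 0 to u) | worsening | worsening | worsening |

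- Persisting Baseline finding: no change in 4 + 6 = 10 of 16, worsening in 6.
- Resolved Baseline finding: no change in 4, improvement in 6, worsening in 6.
- No Other finding at Baseline (b = 0): any new finding has u > 0, so it always shows as worsening.
- Tracked by term: worsening in 16 of 16.

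**Two worked cells.** A grade 2 lid finding that persists, joined by a new grade 2 ulcer, gives max(2, 2) = 2 and is tabulated as 2 to 2, no change. A grade 3 Baseline finding that resolves, followed by a new grade 2 ulcer, is tabulated as 3 to 2, an improvement.

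The counts describe which grade pairings are misclassified. They are not probabilities, because the pairings are not equally likely and the documents give no frequency for Baseline Other findings or for ulceration.

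**Upper bound on the coding work.** 68 recruited subjects × 2 eyes = 136 eyes, each at Baseline and Visit 3.

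**The case against.** The strongest reply is that this row is not the only place where a new ulcer would surface.

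- **Adverse events.** Protocol 9.2 has the investigator review changes in protocol-specific parameters and report clinically relevant untoward ones as adverse events regardless of causality. The glossary counts a potentially sight-threatening event as serious, and SAP 6.3.1 tabulates ocular and serious ocular events by Preferred Term at eye level. A reported ulcer would get its own line there.
- **Recorded detail.** The individual terms and grades are required in the free-text field, and a biomicroscopy listing is planned (16.2.6.2.1). With 54 evaluable subjects, about 108 eyes at Visit 3 can be read line by line.
- **Neighboring items.** Infiltrates are covered in detail for Group 2. The protocol does not say that an eye with an ulcer under Other findings is left ungraded for staining.
- **Unseen shells.** They sit in a separate document, and the SAP does not name *Result* as the shift variable.
- **Descriptive study.** No hypothesis or decision rests on this row.

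Most of this stands, and it limits the point. A reader might infer that a new ulcer could go unseen, or that the study's safety record could look clean when it is not. The documents do not support that: for the event to escape every summary table, it would also have to be judged not clinically relevant, and even then it should be in the listing. Nor do they support a claim that a large share of eyes is affected. Apparent improvement is the narrower case, since a higher-graded Baseline finding would have to resolve within about 30 days.

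What the reply does not do is repair the row. Adverse event reporting depends on the investigator's opinion, and a listing is not a summary. Neither corrects a cell that reads no change. On the variable, a single five-category item matches the *Result* field and nothing in the SAP text suggests another source.

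**Conclusion.** The point holds as a limited one. The Other findings row of Table 14.3.3.2 does not validly show new findings in eyes that already have an Other finding at Baseline. In those eyes, a different sign of equal or lower grade is tabulated as no change, or as improvement if a higher-graded Baseline finding has resolved. Eyes with no Other finding at Baseline are classified correctly.

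The effect is confined to this row. How many eyes it touches cannot be derived from the documents.

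The conclusion rests on two readings: that the shift uses the *Result* grade, and that the shells add no breakdown by term. If the shells already tabulate the specified terms, the remaining change is to say so in the SAP. The correction is worth making because the data are already required and the present row can mislabel the signs the protocol sends to it.

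**What to change.** In SAP 6.3.3 and Tables 14.3.3.1 and 14.3.3.2, supplement or replace the pooled Other findings rows as follows:

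1. Code each entry in the *If Other, Specify* field to a term with its own grade, for each eye, at Baseline and Visit 3.
2. For each term, give the number and percentage of eyes whose finding is new or worse at Visit 3 than at Baseline. Use eyes assessed at both visits as the denominator, in line with SAP 3.2, by group and overall.
3. Give corneal ulceration, recurrent erosion and inferior arcuate staining fixed rows, printed even when the count is zero. An explicit zero is direct evidence of absence, which a pooled grade cannot give.
4. Cross-check every new ulceration or erosion against the listing of treatment-emergent adverse events (16.2.5.1) and explain any mismatch.
5. If the pooled shift is kept, footnote that its two grades may refer to different findings.

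The cost is coding short free text for at most 136 eyes at two visits, and a changed table shell. No new data are collected and no study procedure changes.

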7.3.4.3 BCVA

BCVA will be assessed per standard practice at the Screening/Baseline visit (D1) and at Visit 3 (and at unscheduled and early exit visits, as necessary).

7.3.4.4 Device Deficiencies

Device deficiencies will be collected at the time points specified in Table 4.

7.4 Follow-Up Procedures and Therapy Transitions

In this study, there are no specific follow-up procedures or therapy transitions required. Following study completion, subjects will return to their previous care provider.

Alcon products associated with device deficiencies and/or product-related AEs should, if possible, be returned to Alcon and must include the complaint number, which will be provided by study Sponsor after the case is entered in the study Sponsor’s Global Product Complaint Management System (GPCMS).

Return any recoverable Alcon Product associated with a product-related AE (adverse device effect [ADE], serious adverse device effect [SADE]) or device deficiency to the Sponsor. Procedures vary so Investigators must contact their assigned monitor for detailed guidance. Follow biohazard regulations if the product has touched the eye (i.e., place the product in a biohazard labeled bag). Include the SAE/ADE or device deficiency eCRF in the return package. Maintain a copy of shipment tracking information and all documents submitted with the product.

7.5 Study Timetable / Schedule of Study Assessments

The schedule of study assessments is provided in Table 4.

Table 4. Schedule of Study Assessments

Procedure/ Assessment	Visit 1 Screening + Baseline (Day1)	Visit 2 (phone) 15-day Follow-up (±2 days)	Visit 3 30-day/Exit (±2 days)	Unscheduled Visit/Early Exit
Informed consent	X			
Demographics	X			
Targeted medical history	X			
Targeted concomitant medications	X			
IDEEL-SB questionnaire ^a	X		X	(X)
CL symptom assessed via CLDEQ-8 ^b	X		X	(X)
[REDACTED]	[REDACTED]	[REDACTED]	[REDACTED]	[REDACTED]
Inclusion/Exclusion	X			
Changes in concomitant medications		X	X	X
BCVA	X		X	(X)
[REDACTED]	[REDACTED]	[REDACTED]	[REDACTED]	[REDACTED]
Biomicroscopy findings (include corneal staining)	X		X	(X)
AEs	X	X	X	X
Device deficiencies	X	X	X	X
Exit form	(X)		X	X
Telephone follow-up for compliance check		X		

AE: adverse event; BCVA: best corrected visual acuity; CLDEQ-8: Contact Lens Dry Eye Questionnaire;

IDEEL-SB: Impact of Dry Eye on Everyday Life - Symptom Bother

(X) assessment performed as necessary

^a Assessed in Group 1 (subjects with mild to moderate dry eye)

^b Assessed in Group 2 (subjects with end of day CL-related dryness)

7.6 Deviations from the Clinical Protocol

The Investigator and site personnel should conduct the study in compliance with the protocol and should use continuous vigilance to identify and report protocol deviations. The Investigator may not deviate from the protocol, except when necessary to eliminate an immediate hazard to a study subject, or when the change involves only logistical or administrative aspects of the study. Any significant deviation from the protocol must be reported immediately to the Sponsor or Sponsor's representative and if applicable, to the relevant IRB/IEC, in accordance with the local regulation.

7.7 Clinical Study Termination

The study Sponsor reserves the right to suspend or close the investigational site or suspend or terminate the study in its entirety at any time.

The Investigator may initiate study-site closure at any time, provided there is reasonable cause and sufficient notice is given in advance of the intended termination.

Reasons for the early closure of a study site by the Sponsor or Investigator may include but are not limited to:

- For study termination:
 - Discontinuation of further study treatment development
- For site termination:
 - Failure of the Investigator to comply with the protocol, the requirements of the IRB/IEC or local health authorities, the Sponsor's procedures, or Good Clinical Practice (GCP) guidelines
 - Inadequate or no recruitment (evaluated after a reasonable amount of time) of subjects by the Investigator
 - Total number of subjects included earlier than expected

If the clinical study is prematurely terminated or suspended by the study Sponsor:

- The study Sponsor (or its acting representative) shall:
 - Immediately notify the Investigator(s) and subsequently provide instructions for study termination.
 - Inform the Investigator and the regulatory authorities of the termination/suspension and the reason(s) for the termination/suspension.
- The Investigator shall:
 - Promptly notify the IRB/IEC of the termination or suspension and of the reasons.
 - Provide subjects with recommendations for poststudy treatment options as needed.

7.8 Subject Compensation

Where permitted by the IRB/IEC, study subjects will be compensated for participation.

8 DATA COLLECTION AND ANALYSIS

8.1 Subject Populations for Analysis

Two analysis data sets will be defined:

- The Full Analysis Set (FAS) will include all subjects/eyes exposed to at least one dose of Systane Ultra PF. The Full Analysis Set will serve as the primary analysis set for all effectiveness and safety analyses.
- The Per Protocol (PP) population is a subset of the FAS and will exclude subjects with major protocol deviations. The PP population will be a supportive set for effectiveness analyses, as necessary.

8.2 Statistical Methods

This section is a summary of the planned statistical analyses. A Statistical Analysis Plan will be finalized prior to database lock and will include a more technical and detailed description of the statistical analyses described in this section.

Statistical analyses will be presented by group (Group 1: subjects with mild to moderate dry eye; Group 2: subjects with end of day CL-related dryness).

There is no statistical hypothesis for the endpoints in this study. Appropriate descriptive statistics will be computed and presented for all categorical and continuous endpoints.

- For categorical variables, the number and percentage of subjects/eyes within each category of interest will be presented.
- For continuous variables, the number of subjects/eyes with non-missing data, mean, standard deviation, range, median, minimum, and maximum will be presented.
- There will be no imputation for missing data.

All visual acuity results will be presented in logarithm of the minimum angle of resolution (logMAR) scale after applying appropriate transformations/conversions.

